1.2 GLS-5700

GLS-5700 contains a single plasmid, pGX7201, in sterile saline salt citrate buffer (SSC).

Common name: pGX7201

Chemical name: pGX7201 is a circular, double stranded, deoxyribonucleic acid plasmid consisting of 5066 base pairs.

Distinguishing name: This is a eukaryotic expression plasmid containing DNA encoding for pre-membrane and envelope (prME) proteins of the Zika virus. pGX7201 incorporates a consensus prME sequence of published Zika virus clinical isolate strains. The prME sequence has been codon optimized for mammalian expression. The transcription unit is controlled by a synthetic CMV promoter and elements required for replication and selection in *E coli*, namely a pUC origin of replication (pUC-Ori) and kanamycin resistance gene (KanR), respectively.

1.3 Dose and Regimen Rationale

The optimal dose and dosing regimen for GLS-5700 are as yet uncharacterized. In addition to safety, this study will assess two different doses of vaccine to evaluate optimal humoral and cellular immune responses to Zika prME. Based on prior experience with other DNA vaccines, there may be a plateau effect above 2 mg for DNA vaccines administered by EP. Preclinical studies of pGX7201 (the plasmid that comprises GLS-5700) in rhesus macaques assessed high (2 mg/vaccination) and low (0.5 mg/vaccination) doses with similar immunogenicity. No significant difference was seen in mice between doses of 12.5 μ g and 25 μ g/dose. Additionally, robust antibody and T-cell immune responses in humans were elicited with a dose of 2 mg/vaccination with a similar DNA construct in a Phase I dose-ranging study for the treatment of cervical dysplasia related to HPV cervical infection [25, 26]. Assessment of antibody and T-cell responses following each vaccination will determine the immune response to vaccination. Follow-up after the primary vaccination series will determine the longevity of immunogenicity of the vaccine.

1.4 Risks/Benefit Assessment

In accordance with the International Conference on Harmonisation (ICH), this study has been designed to minimize risk to study participants. Potential risks of study products and administration from studies using similar plasmids with the identical DNA backbone are listed in **Table 1.4**.

The potential side effects of treatment with the investigational products may include but not limited to discomfort related to the vaccine administration and electroporation technique such as local edema, swelling, or pain. Systemic side effects observed with vaccines based on the identical backbone have been demonstrated to be generally minimal in more than 725 participants. Since the volunteers in this clinical trial have unknown risk for exposure to Zika virus, no direct benefit is expected. The potential benefit is to determine whether this vaccine could generate immune responses with potential to be sufficient as prophylactic treatment for those at risk for Zika virus infection.

Table 1.4: Summary of Reported Adverse Events of DNA Vaccines Delivered IM+EP or ID+EP with CELLECTRA®

Common	
 Mild to moderate administration site pain, erythema, tenderness, swelling, induration Malaise/fatigue, myalgia, or headache in the first few days following injection Visible lesion(s) at the injection site, such as erythematous papules with eschar, hypopigmentation, hyperpigmentation, or scar (ID administration only)
Less common	
 Administration site bruising/ecchymosis, hematoma or pruritus Arthralgia or nausea Injection site hematoma, bruising/ecchymosis, laceration, other transient lesions, or bleeding related to the injection procedure
Uncommon or rare	
 Administration site, laceration, other transient lesions, or bleeding related to the injection procedure Severe administration site pain or tenderness Rash following injection/EP Scar formation (ID administration) Vasovagal reaction/lightheadedness/dizziness related to the injection/EP procedure Transient changes in clinical laboratory values
Unknown frequency or theoretical potential risks	
 Severe localized administration site reaction, such as sterile abscess or secondary bacterial infection Allergic reaction, including urticaria, angioedema, bronchospasm, or anaphylaxis Chills, flu-like syndrome Muscle damage at the administration site Autoimmune disease Electrical injury Disruption of function of implanted electronic medical devices Exacerbation of cardiac arrhythmia Effects on the fetus and on pregnancy

The full safety monitoring plan is described in detail in the Evaluation of Safety and Management of Toxicity section below (Section 7).

2. HYPOTHESIS AND STUDY OBJECTIVES

2.1 Hypothesis

GLS-5700 administered intradermally (ID) followed by EP will be safe, well tolerated and immunogenic in dengue virus-naïve adults.

2.2 Primary Objectives

- Evaluate the safety and tolerability of GLS-5700 when administered by ID injection followed by EP in healthy dengue virus-naïve adult participants within 14 days post final vaccination.

Primary Safety Endpoints

- Incidence of adverse events classified by system organ class (SOC), preferred term (PT) severity, and relationship to study treatment and schedule to 14 days post final vaccination in dengue virus-naïve adults
- Administration (injection) site reactions (described by frequency and severity grade) and administration site pain to 14 days post final vaccination
- Changes in safety laboratory parameters described by frequency and severity grade (e.g., liver panel tests, vital signs)

2.3 Secondary Objectives

- Evaluate the safety to 1 year post vaccination of GLS-5700 in dengue virus-naïve adults
- Evaluate the cellular and humoral response of GLS-5700 when delivered ID followed by EP in dengue virus-naïve adults

Secondary Immunologic Endpoints

- Binding antibody titers to the Zika envelope (E) protein as measured by ELISA
- Neutralizing antibody titers against Zika virus as measured in viral neutralization assay
- Antigen specific cellular immune responses to Zika virus as determined by Interferon-gamma (IFN- γ) ELISpot and/or Intracellular Staining (ICS) assays

2.4 Exploratory Objectives

- Explore whether end point antibody titers are dose related.
- Explore the time to onset and longevity of immune responses, both humoral and cellular
- Explore if increasing dose levels of GLS-5700 more rapidly induce cellular and humoral immunity
- Explore the epitope specificity for T cell reactions of GLS-5700 to Zika virus

Exploratory Endpoints

- Comparison of ELISA, neutralization titers, IFN- γ ELISpot, and ICS responses across different vaccine regimens
- Other analyses as indicated to assess protective mechanisms against Zika virus.
- Epitope mapping of CD4+ and CD8+ T lymphocyte responses

3. STUDY DESIGN

This is a Phase I open-label, dose-ranging study to assess the safety, tolerability, and immunogenicity of GLS-5700 in dengue virus-naïve adults. Eligible participants who consent to participate will be administered GLS-5700 via ID injection followed immediately by EP using the CELLECTRA® 3P Adaptive Constant Current Electroporation device.

Prospective participants who read and sign the ICF will be screened for eligibility for up to 30 days prior to their first dose. Screening evaluation will consist of a medical history, vital signs including height and weight, ECG, and laboratory evaluations. Participants without a history of exclusionary conditions, not clinically significant or normal ECG, and Grade 0-1 laboratory values (per the Toxicity Grading Scale for Healthy Adults Appendix B) for CBC, serum chemistry, and CPK, will be eligible for participation in the trial.

Evaluation of ID administration of GLS-5700:

Group 1 Participants (n=20) will be administered 1 mg GLS-5700 DNA/dose given as an ID injection followed by EP with the CELLECTRA®-3P device. Participants will receive a 3-dose series with immunizations at 0, 4, and 12 weeks.

Group 2 Participants (n=20) will be administered 2 mg GLS-5700 DNA/dose given as two ID injections per immunization followed by EP with the CELLECTRA®-3P device. Participants will receive a 3-dose series with immunizations at 0, 4, and 12 weeks.

See **Tables S1 and S2** for a summary of study treatments and dosing schedule.

Safety assessments: All participants will be monitored for

- Local and systemic adverse events (AE's) at each study visit.
- Laboratory related AE's following each vaccination.

Immunogenicity assessments:

The study will explore humoral and cell mediated immune responses in blood samples collected at the following times:

- Day 0 (prior to 1st dose of vaccine)
- Week 1 and week 4 post 1st vaccination
- Week 6 and 12 (2 and 8 weeks post 2nd vaccination)
- Week 14 and 20 (2 weeks and 8 weeks post 3rd vaccination)
- Weeks 36 and 60

3.1 Treatment Progression Scheme / Interim Safety Monitoring

This study will utilize a treatment progression scheme similar to WRAIR-2274 (assessment of GLS-5300 against MERS CoV) to assess and ensure the safety of each dose level of vaccine as follows.

Participants will be contacted by telephone to report reactions the day following the 1st vaccination to determine whether there are any AE's or other reactions. If no vaccine associated AEs requiring expedited reporting have occurred for the first 5 participants enrolled at 1 mg, then enrollment of the remainder of Group 1 at 1 mg/dose can proceed. Progression to the 2nd dose of vaccine at 1 mg/dose or enrollment of Group 2 at 2 mg/dose will require safety assessment as detailed below.

Safety laboratory assessments will be performed 1 week after the 1st dose of vaccine and 2 weeks after the 2nd and 3rd doses for all study participants, as appropriate. If no vaccine associated Grade 3 or Grade 4 AEs or any Serious Adverse Events (SAE) are encountered for the first 5 participants enrolled at 1 mg dose after review of their safety data, then enrollment into the 2 mg group can proceed. If there are no vaccine associated Grade 3 or 4 or serious safety events noted for the first 5 participants 24 hr post administration of 2 mg, then dosing will continue. Safety labs will be reviewed for the 1st 5 participants at the 2 mg dose by the monitoring committee. Safety labs will be reviewed monthly thereafter.

Review of safety labs will be conducted by a safety monitoring committee consisting of the study medical monitor with input from the site PI. The IRB/CER will be provided a summary statement of each safety review. The Safety Monitoring Committee (SMC) will meet to review safety laboratory assessments after 5 persons have received vaccine at each dose level. The committee will meet between 2-5 business days following the collection of safety labs for all 5 persons at the respective dose level. SMC meetings thereafter will occur on an ad hoc basis in response to any potential safety concerns.

4. SELECTION AND ENROLLMENT OF PARTICIPANTS

4.1 Recruitment of Participants

Adult volunteers will be recruited for the study.

4.2 Inclusion Criteria

- a. Age 18-65 years;
- b. Able to provide consent to participate and having signed an Informed Consent Form (ICF);
- c. Able and willing to comply with all study procedures;
- d. Women of child-bearing potential agree to use medically effective contraception (oral contraception, barrier methods, spermicide, etc.), or have a partner who is sterile from enrollment to 3 months following the last injection, or have a partner who is medically unable to induce pregnancy.
- e. Sexually active men who are considered fertile must agree to use either a barrier method of contraception during the study, and agree to continue the use for at least 3 months following the last injection, or have a partner who is permanently sterile or medically unable to become pregnant;
- f. Normal screening ECG or screening ECG with no clinically significant findings;

- g. Screening labs must be within normal limits or have only Grade 0-1 findings, except that creatinine may be grade 2 at baseline;
- h. No history of clinically significant immunosuppressive or autoimmune disease.
- i. No history of dengue virus vaccination or illness; no history of yellow fever vaccination
- j. Dengue seronegative at baseline by screening laboratory evaluation
- k. Not currently or within the previous 4 weeks taking immunosuppressive agents (excluding inhaled, topical skin and/or eye drop-containing corticosteroids, low-dose methotrexate, or prednisone at a dose less than 10 mg/day or steroid dose-equivalent).

4.3 Exclusion Criteria

- a. Administration of an investigational compound either currently or within 30 days of first dose;
- b. Previous receipt of an investigational product for the treatment or prevention of Zika virus infection except if participant is verified to have received placebo;
- c. Administration of any vaccine within 4 weeks of first dose;
- d. Administration of any monoclonal or polyclonal antibody product within 4 weeks of the first dose
- e. Administration of any blood product within 3 months of first dose;
- f. Pregnancy or breast feeding or have plans to become pregnant during the course of the study;
- g. Positive serologic result for dengue virus (any serotype) or history of receipt of either dengue virus or yellow fever virus vaccination at any time in the past;
- h. Positive serologic test for HIV, hepatitis B surface antigen (HBsAg); or any potentially communicable infectious disease as determined by the Principal Investigator or Medical Monitor;
- i. Positive serologic test for hepatitis C (exception: successful treatment with confirmation of sustained virologic response);
- j. Baseline evidence of kidney disease as measured by creatinine greater than 1.5 (CKD Stage II or greater);
- k. Baseline screening lab(s) with Grade 2 or higher abnormality;
- l. Chronic liver disease or cirrhosis;
- m. Immunosuppressive illness including hematologic malignancy, history of solid organ or bone marrow transplantation;
- n. Current or anticipated concomitant immunosuppressive therapy (excluding inhaled, topical skin and/or eye drop-containing corticosteroids, low-dose methotrexate, or corticosteroids at a dose greater than 10 mg/day or steroid dose-equivalent);
- o. Current or anticipated treatment with TNF- α inhibitors such as infliximab, adalimumab, etanercept;
- p. Prior major surgery or any radiation therapy within 4 weeks of group assignment;
- q. Any pre-excitation syndromes, e.g., Wolff-Parkinson-White syndrome;

- r. Presence of a cardiac pacemaker or automatic implantable cardioverter defibrillator (AICD)
- s. Metal implants within 20 cm of the planned site(s) of injection;
- t. Presence of keloid scar formation or hypertrophic scar as a clinically significant medical condition at the planned site(s) of injection.
- u. Prisoner or participants who are compulsorily detained (involuntary incarceration) for treatment of either a physical or psychiatric illness;
- v. Active drug or alcohol use or dependence that, in the opinion of the investigator, would interfere with adherence to study requirements or assessment of immunologic endpoints; or
- w. Not willing to allow storage and future use of samples for Zika virus related research
- x. Any illness or condition that in the opinion of the investigator may affect the safety of the participant or the evaluation of any study endpoint.

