- i. Positive serologic test for hepatitis C (exception: successful treatment with confirmation of sustained virologic response);
- j. Baseline evidence of kidney disease as measured by creatinine greater than 1.5 (CKD Stage II or greater);
- k. Baseline screening lab(s) with Grade 2 or higher abnormality, except for Grade 2 creatinine;
- l. Chronic liver disease or cirrhosis;
- m. Immunosuppressive illness including hematologic malignancy, history of solid organ or bone marrow transplantation;
- n. Current or anticipated concomitant immunosuppressive therapy (excluding inhaled, topical skin and/or eye drop-containing corticosteroids, low-dose methotrexate, or prednisone at a dose greater than 10 mg/day or steroid dose-equivalent);
- o. Current or anticipated treatment with TNF- α inhibitors such as infliximab, adalimumab, etanercept;
- p. Prior major surgery or any radiation therapy within 4 weeks of group assignment;
- q. Any pre-excitation syndromes, e.g., Wolff-Parkinson-White syndrome;
- r. Presence of a cardiac pacemaker or automatic implantable cardioverter defibrillator (AICD)
- s. Metal implants within 20 cm of the planned site(s) of injection;
- t. Presence of keloid scar formation or hypertrophic scar as a clinically significant medical condition at the planned site(s) of injection.
- u. Prisoner or participants who are compulsorily detained (involuntary incarceration) for treatment of either a physical or psychiatric illness;
- v. Active drug or alcohol use or dependence that, in the opinion of the investigator, would interfere with adherence to study requirements or assessment of immunologic endpoints; or
- w. Not willing to allow storage and future use of samples for Zika virus related research
- x. Any illness or condition that in the opinion of the investigator may affect the safety of the participant or the evaluation of any study endpoint.

Table S2. Schedule of Events: 3 vaccinations

Tests and Observations	Screen (Day -7 to -30)	Day0	Day1	Wk1 (±2d)	Wk4 (±5d)	Wk6 (±5d)	Wk12 (±5d)	Wk14 (±5d)	Wk20 (±10d)	Wk36 (±10d)	Wk60 (±10d) / Early termination
Clinical Assessments											
Consent	X										
Med history	X	X									
Demographics	X										
Travel hx ^a	X										
Medications ^b	X	X		X	X	X	X	X	X	X	
Phys Exam ^c	X	X		X	X	X	X	X	X	X	
Vital signs ^c	X	X		X	X	X	X	X	X	X	
Laboratory Assessments											
12-lead ECG	X										
CBC w/diff	X			X		X		X			
Chemistries ^d	X			X		X		X			
Serologies ^e	X										
Pregnancy ^f	X	X			X		X				

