3.5.1. Inclusion Criteria

Subjects must meet all of the following criteria to be eligible for this study.

- a. Age 18-65 years;
- b. Able to provide consent to participate and having signed an Informed Consent Form (ICF);
- c. Able and willing to comply with all study procedures;

Statistical Analysis Plan

- d. Women of child-bearing potential agree to use medically effective contraception (oral contraception, barrier methods, spermicide, etc.), or have a partner who is sterile from enrollment to 3 months following the last injection, or have a partner who is medically unable to induce pregnancy.
- e. Sexually active men who are considered fertile must agree to use either a barrier method of contraception during the study, and agree to continue the use for at least 3 months following the last injection, or have a partner who is permanently sterile or medically unable to become pregnant;
- f. Normal screening ECG or screening ECG with no clinically significant findings;
- g. Screening labs must be within normal limits or have only Grade 0-1 findings, except that creatinine may be grade 2 at baseline;
- h. No history of clinically significant immunosuppressive or autoimmune disease.
- i. No history of dengue virus vaccination or illness; no history of yellow fever vaccination
- j. Dengue seronegative at baseline by screening laboratory evaluation
- k. Not currently or within the previous 4 weeks taking immunosuppressive agents (excluding inhaled, topical skin and/or eye drop-containing corticosteroids, low-dose methotrexate, or prednisone at a dose less than 10 mg/day or steroid dose-equivalent).

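### As written, inclusion k and exclusion n exempt steroid doses in opposite directions: no current systemic dose passes both, and for anticipated-only use n excludes 10 mg/day or less but exempts more.

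*Protocol*

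**What the plan says.** Inclusion k asks that a volunteer not be on immunosuppressants now or in the preceding 4 weeks. It then lists what does not count: inhaled, topical and eye-drop steroids, low-dose methotrexate, "or prednisone at a dose less than 10 mg/day or steroid dose-equivalent". The wording is the same in the Synopsis, Protocol 4.2 and SAP 3.5.1.

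Exclusion n bars immunosuppressive therapy that is current or anticipated, again with exceptions in parentheses. In Protocol 4.3 the list ends "or corticosteroids at a dose greater than 10 mg/day or steroid dose-equivalent". In the Synopsis it ends "or prednisone at a dose greater than 10 mg/day or steroid dose-equivalent", and SAP 3.5.2 repeats that. In all three copies the bracket closes after the steroid clause, so grammatically the clause is an exception to the bar.

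The criteria apply jointly. SAP 3.5.1 states "Subjects must meet all of the following criteria to be eligible for this study", and SAP 3.5.2 makes any single exclusion disqualifying.

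Neighbouring criteria bear on the same volunteers:
- inclusion h: "No history of clinically significant immunosuppressive or autoimmune disease"
- exclusion m: "Immunosuppressive illness including hematologic malignancy, history of solid organ or bone marrow transplantation"
- exclusion o: TNF-alpha inhibitors, "such as infliximab, adalimumab, etanercept"
- exclusion x: "Any illness or condition that in the opinion of the investigator may affect the safety of the participant", or may affect the evaluation of an endpoint

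None of these sets a steroid dose. Protocol 6.10 has immunosuppressants recorded but does not restrict them. Protocol 6.11 restricts only vaccines and antibody products.

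**The concern.** An inclusion criterion and its matching exclusion criterion should describe the same people from two sides. Here one tolerates doses below 10 mg/day and the other tolerates doses above it. Sites cannot apply both as written and still give effect to the allowance in k. For planned use, the text screens out the lower doses and lets the higher ones through.

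Two things are at stake. First, the secondary endpoints (Protocol 2.3) are binding and neutralizing antibody titers and T-cell responses, so the rule on immunosuppressants should be unambiguous. Exclusion n puts no time limit on anticipated use, and Protocol 3 schedules eight post-baseline immune samples (weeks 1, 4, 6, 12, 14, 20, 36 and 60). Second, eligibility feeds an analysis set. Protocol 4.4, in its list of discontinuation reasons, counts failure to meet the entry criteria as a protocol violation. Protocol 8.1 admits to the per-protocol set only participants without violations.

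**Working it through.** No sample size, power or alpha figure is involved. The check applies the two criteria literally to a systemic prednisone-equivalent dose d > 0 (mg/day). Inhaled, topical and eye-drop steroids are exempt under both criteria and play no part.

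**Inputs**
- k (Protocol 4.2): covers current use and the previous 4 weeks; met if d < 10.
- n (Protocol 4.3): covers current and anticipated use; not triggered if d > 10.
- Eligible on both: k met and n not triggered (SAP 3.5.1, 3.5.2).

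**Current use.** Eligibility needs d < 10 and d > 10 together. No dose meets both conditions. At exactly 10, k fails and n is triggered. A run through every dose from 0.1 to 200 mg/day in steps of 0.1 found none that passes both.

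**Recent use only** (stopped within the previous 4 weeks, none planned). n is silent, so eligibility needs d < 10. This is the only setting in which the allowance in k has effect.

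**Anticipated use only.** k is silent, so eligibility needs d > 10.

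The doses below only illustrate the logic; they are not a frequency.

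| d (mg/day) | Current use | Recent use only | Anticipated only |
|---|---|---|---|
| 5 | no (meets k, triggers n) | yes | no |
| 9.9 | no (meets k, triggers n) | yes | no |
| 10 | no (fails k, triggers n) | no | no |
| 10.1 | no (fails k, exempt from n) | no | yes |
| 20 | no (fails k, exempt from n) | no | yes |

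**Alternative reading of n.** Suppose the bracket were meant to close after low-dose methotrexate, so that the steroid clause is a bar and not an exception. Then n would bar d > 10, and its cut-off would differ from that of k only at d = 10, which fails k when current and passes n when anticipated. The direction would agree, but the boundary would not.

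**Agent.** Protocol 4.3 names *corticosteroids* and gives 10 mg/day without a reference steroid. The Synopsis and SAP 3.5.2 name *prednisone*. This does not alter the table, but it is a further difference between copies of one rule.

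**Analysis sets.** Under Protocol 8.1 the safety set depends only on receiving at least one vaccination. The immunogenicity analysis of all participants with evaluable data (Protocol 8.4, SAP 5.4) does not depend on k or n once a person is enrolled. The precision tables depend on N = 40. Per-protocol membership is where a failed criterion counts: SAP 7.2 bases immunogenicity on the per-protocol and mITT sets, and Protocol 8.1 makes mITT supportive of per-protocol.

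**The case against.** The best defence is that this is a plain slip that experienced sites will read sensibly, and that the opposition depends on where a bracket closes. That is fair as an account of how it arose. It does not settle the text: the bracket sits in the same place in all three copies, so there is no correct copy to defer to, and moving it still leaves exactly 10 mg/day unresolved.

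The second defence is that almost nobody falls into the gap, and this largely stands. For current use the two criteria exclude too many people, not too few. The opening is confined to a volunteer who is not on steroids now, plans more than 10 mg/day, has no condition under h, m or o, and is not stopped under x. The primary objective also describes healthy adults. None of those criteria supplies a steroid dose rule, though, and x rests on case-by-case judgment.

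A reader might infer three stronger things that the documents do not support:
- *That people now taking more than 10 mg/day can enrol.* Inclusion k keeps them out.
- *That the SAP 6.1 listing would show planned lower doses as violations and miss planned higher ones.* SAP 6.1 says only that violations are listed, SAP 4.5 takes deviations from the CRF, and Protocol 6.10 records medications taken, not plans. No derivation from a planned dose is described.
- *That response rates would be distorted.* The documents give neither the number of such volunteers nor an effect size.

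**Conclusion.** The inconsistency is real and should be corrected. As written, the allowance in k cannot operate for current use, because no non-zero systemic dose passes both criteria. For anticipated-only use, n excludes 10 mg/day or less and exempts doses above it.

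Its size is modest. It concerns eligibility logic and, through Protocol 4.4 and 8.1, who counts as per-protocol. SAP 4.4 removes only major violations, so under the SAP the second effect depends on how the violation is classed. The stated precision figures and the all-evaluable immunogenicity analysis are not affected, and no change in any response rate is claimed.

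The conclusion assumes that the parenthesis in n is read literally as a list of exceptions and that all criteria apply jointly, as the SAP states. Which direction or threshold was intended cannot be determined from the documents and is not for a statistical review to decide.

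**What to change.** Reconcile exclusion n with inclusion k on four points:
- direction: which side of the threshold is exempt
- boundary: how exactly 10 mg/day is treated
- agent: prednisone or corticosteroids, with the reference for dose equivalence
- timing: current, recent and anticipated use

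Then state the one rule identically in the Synopsis, Protocol 4.2 and 4.3, and SAP 3.5.1 and 3.5.2. The clinical team decides which rule stands. The cost is wording changes in the protocol and SAP; no participants, procedures or data are added.
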